### 3.1.7 COST-EFFECTIVENESS

This study seeks to evaluate the cost-effectiveness of a fully-automated intervention for diabetes prevention that does not require any human support outside of the maintenance and support of the app itself compared to a standard of care control group consisting of a human coach-based diabetes prevention program (hDPP) delivered via in-person or via distance learning modalities.

## 3.2 PRIMARY ENDPOINT

The trial is designed as a non-inferiority trial to evaluate whether the Sweetch dDPP is at least as effective as hDPPs on participant attainment of the CDC's benchmark for type 2 diabetes risk reduction, defined as one or more of the following:

- At least 5% weight loss by 12 months
- At least 4% weight loss at 12 months and at least 150 minutes/week of physical activity measured using monthly serial Actigraphy and averaged over months 1-11)
- At least a 0.2% reduction in hemoglobin A1C by 12 months (for participants whose A1C result obtained at baseline study visit is between 5.7% and 6.4%).

Thus, the prospectively defined primary endpoint will be a binary endpoint at 12 months, defined as 1 if at least one of the CDC "success" outcome measures is achieved and 0 if none are achieved. The primary endpoint was selected to align with the current CDC standards for full recognition of DPP programs (effective May, 2021). According to the CDC, participants may demonstrate type 2 diabetes risk reduction by fulfilling one or more of the above outcomes, and, given the broad range of eligibility criteria for the DPP (see Section 5.1), not all DPP participants are eligible to demonstrate success using each of three outcomes in our composite endpoint. Specifically, the A1C change measure can only be used for participants whose baseline measure is in the prediabetic range of 5.7% to 6.4%. These standards require that at least 60% of participants in a given DPP meet the endpoint for attainment of full recognition in order to become a Medicare DPP supplier. The CDC's Standards and Operating Procedures are subject to change during the course of the study. Should the benchmarks for type 2 diabetes risk reduction change prior to completion of the trial, to the extent possible (i.e. assuming we have collected required data during the trial), we will also analyze our outcomes to align with the updated benchmark.

## 3.3 SECONDARY ENDPOINTS

Secondary endpoints will include:

- Primary endpoint assessed using self-reported PA data in lieu of objectively measured PA data (Actigraphy).
  - In this trial, PA will be assessed using both participant self-reported data and Actigraphy. While the CDC relies on participant self-reported PA data for outcome assessment, in this trial, there is a potential bias introduced from using self-reported PA data alone since the dDPP arm will have access to objective PA data while the hDPP group may or may not (depending on their personal use of wearable devices or fitness tracking apps). Studies have shown over-estimation of PA by self-report. Considering that the CDC accepts self-reported PA data, we

will also analyze results of the primary endpoint using self-reported PA data collected at same interval as serial Actigraphy.

- Change in A1C from baseline to 6 months and 12 months
- Absolute and percentage weight change from baseline to 6 and 12 months
- Changes in physical activity measures (average minutes/week of physical activity, MET-hours per week of physical activity, average number of steps per day) at 6 months and 12 months
- Incident type 2 diabetes (A1C  $\geq 6.5\%$ )
- Engagement level
  - The **dDPP engagement score** will be calculated as the percentage of full weeks during which the app was installed and a) both push notifications and motion sensors were enabled OR b) participant accessed any content within the app.
  - The **hDPP engagement score** will be calculated as a percentage of sessions attended. Per CDC definitions of engagement, the number of required hDPP sessions for months 1-6, 7-12, and 1-12 will be 8, 3, and 11, respectively. For participants who attend more than the required number of sessions across each of these intervals, the engagement score will be capped at 100%. A participant who attends 4 out of 8 sessions in months 1-6 and 1 out of 3 sessions in months 7-12 would receive an engagement score of 50% (4 out of 8 sessions in months 1-6), 33% (1 out 3 sessions in months 7-12), and 45% (5 out of 11 sessions in months 1-12).
  - Engagement will be analyzed across months 1-6, 7-12, and 1-12 months. For both arms, full weeks will be defined as the number of complete weeks between baseline visit and the 6 month or 12 month visit, respectively. For example, a participant who is followed for 25.4 weeks during months 1-6 and 26.2 weeks during months 7-12 would be considered to have 25 and 26 full weeks on study, respectively.
- Percentage of **program completers**
  - The CDC defines **completers** for the hDPP to be participants who attend at least 8 sessions in months 1-6 and whose time from first session held by the cohort to the last session attended by the participant is at least 9 months. For participants in the hDPP arm, we will evaluate the percentage of completers in the program according to the CDC's definition. Similarly, for the dDPP arm, completers will be defined as participants who meet the engagement definition for at least 8 weeks in months 1-6 AND whose time between app installation and last week of engagement is at least 9 months.
- Acceptability of digital and in-person DPPs
- Correlation of self-reported and objectively measured PA data
- Change in overall well-being scores
- Cost-effectiveness

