### 3.1.2 ENGAGEMENT AND PROGRAM COMPLETION

Secondary objectives of the trial will be a) to compare engagement with digital vs. human coach-based DPPs and evaluate whether between-group differences in clinical outcomes are mediated by engagement and b) to compare acceptability of digital vs. human coach-based DPPs. We will define an engagement score (out of 100%) for the hDPP based on the percentage of total number of sessions attended, using the most current CDC engagement definitions at the time of completion of the study. Percentage engagement will be defined out of a total of 8 sessions in month 1-6 and 3 sessions in month 7-12, for a total of 11 sessions across months 1-12. We will define an engagement score (out of 100%) for the dDPPs based on percentage of full weeks during which the app is installed and a) both push notifications and motion sensors are enabled or b) the participant accesses any component within the app for months 1-6 and months 7-12. We hypothesize that participant's level of engagement, regardless of treatment assignment, will be associated with the primary endpoint (attainment of CDC benchmark for diabetes risk reduction). We hypothesize that dDPPs will be considered more acceptable by participants owing to greater convenience, more timely support, and the provision of more effective tools for weight, diet, and activity monitoring.

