## 6.2 CONTROL ARM DESCRIPTION

Participants randomized to the hDPP arm will be provided a list of participating CDC recognized lifestyle change programs within a 25 mile radius of the main study site. Eligible programs will be identified using the CDC's Recognized Lifestyle Change Program Website, which maintains a registry of recognized programs.

For this trial, eligible local programs must meet the following criteria:

- Have preliminary or full recognition status by the CDC (i.e. identifiable on the CDC's online registry)
- Provide in-person or *synchronous* distance learning (video conferencing) modalities
- Expressed interest in participating in the clinical trial
- Agree to share outcomes and attendance data (per CDC reporting requirements) using study team's electronic data capture form.

To achieve preliminary or full recognition, local DPPs must adhere to the CDC's Diabetes Prevention Recognition Program Standards and Operating Procedures. Sessions are delivered by trained lifestyle coaches and each site offers at least 16 sessions during the first 6 months (core phase) and 6 sessions during the last 6 months (core maintenance phase). Each program follows a CDC approved curriculum, using either the 2012 National DPP curriculum or the more recent CDC-developed PreventT2 curriculum (majority). Core sessions are held weekly for months 0-6, then typically bi-monthly for the core maintenance sessions in months 7-12, which is divided into two intervals (months 7-9 and months 10-12). Programs are required to offer at least 6 sessions during the last 6 months (3 per interval).

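### dDPP engagement and completion can be met on phone settings alone while hDPP needs attended sessions, so the between-arm engagement results partly reflect the metric

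*Combined protocol and SAP*

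**What the plan says.** **dDPP score (Sections 3.1.2 and 3.3).** The planned figure "will be calculated as the percentage of full weeks during which the app was installed and a) both push notifications and motion sensors were enabled". The second limb reads "OR b) participant accessed any content within the app". The two limbs are alternatives, so either one qualifies a week.

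**hDPP score (Section 3.3).** The score "will be calculated as a percentage of sessions attended", and "the number of required hDPP sessions for months 1-6, 7-12, and 1-12 will be 8, 3, and 11, respectively". Also, "For participants who attend more than the required number of sessions across each of these intervals, the engagement score will be capped at 100" per cent. Section 6.2 says that "each site offers at least 16 sessions during the first 6 months (core phase) and 6 sessions during the last 6 months".

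**Completers (Section 3.3).** hDPP follows the CDC rule: 8 attended sessions in months 1-6, and at least 9 months from the cohort's first session to the participant's last one. For dDPP, "completers will be defined as participants who meet the engagement definition for at least 8 weeks in months 1-6", with at least 9 months from installation to the last engaged week. The settings limb counts towards this.

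**Use of the scores.** The Synopsis and Section 3.1.2 compare engagement between arms, and the Synopsis adds completion. Both also aim to "evaluate whether between-group differences in clinical outcomes are mediated by engagement". Section 2.2 expects greater engagement with the dDPP. Section 9.3 uses completers in each arm as the per-protocol set for benchmarking against CDC standards. Section 9.4 gives no mediation model, no common scale and no active-use sensitivity analysis.

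**The concern.** The two percentages carry the same name but measure different things. One counts attendance against a reduced and capped requirement. The other counts calendar weeks, and a week can qualify through phone permissions with no use of the app. Each may suit reporting inside its own programme. The difficulty arises when one is subtracted from the other, or when engagement is asked to explain a difference in outcome between arms.

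At stake are the between-arm engagement and completion results, the mediation result, and the dDPP completers who are set against the 60% benchmark. The trial is open-label, the statistician is unmasked, and the study team sees app logs in real time (Section 6.4). A change of metric made after results are seen would be hard to defend, so it should be settled beforehand.

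**Working it through.** **Inputs.** hDPP denominators 8, 3 and 11, capped at 100% (Section 3.3). Sessions offered: at least 16 and then 6 (Section 6.2). dDPP denominators 25 and 26 full weeks, 51 in all, from the worked example in Section 3.3. Kit delivery 8-12 days after randomisation (Section 6.1). Full weeks are counted from the baseline visit (Section 3.3).

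**Step 1. Reproduce the plan's own example.** For 4 of 8 and 1 of 3 sessions: 4/8 = 50%, 1/3 = 33%, 5/11 = 45%. These match Section 3.3.

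**Step 2. Same active contact, months 1-6.** Take active contact in 8 different weeks.
- hDPP: 8/8 = 100%. This is 8/16 = 50% of the minimum offered.
- dDPP, settings limb unmet in all 17 other weeks: 8/25 = 32%.
- dDPP, settings left on throughout: close to 100%. If installation waits for the kit, one or two early weeks cannot count, giving 24/25 = 96% or 23/25 = 92%.

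One pattern of active use therefore maps to 100% in hDPP and to anything from 32% to nearly 100% in dDPP.

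**Step 3. Same active contact over the year.** Eleven contacts give 11/11 = 100% in hDPP. In dDPP they give 11/51 = 22% if the settings limb is unmet in all other weeks, and more otherwise.

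**Step 4. No active contact after set-up.** hDPP scores 0% and the participant is not a completer. dDPP with settings left on again scores close to 100%, and the participant meets the 8-week completer count.

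**Step 5. Illustration of direction (assumed values, not trial data).** Let active weeks in months 1-6 follow the same Binomial(25, p) in both arms, with one session per active hDPP week. Let a share s of dDPP participants qualify through settings in every week. This is an upper case, because it ignores kit delay. The mean hDPP score is the average of min(X/8, 1), taken from 200,000 simulated draws. The mean dDPP score is s + (1 - s)p.

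| p | hDPP mean | dDPP, s = 0 | s = 0.25 | s = 0.50 | s = 0.75 |
|---|---|---|---|---|---|
| 0.20 | 61.6% | 20% | 40% | 60% | 80% |
| 0.32 | 88.5% | 32% | 49% | 66% | 83% |

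At p = 0.20, hDPP leads for s up to 0.50 and dDPP leads at 0.75. At p = 0.32, hDPP leads throughout.

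For the 8-unit part of the completer rule at p = 0.32, the hDPP share is 57%. The dDPP share is s + (1 - s) × 0.574, that is 57%, 68%, 79% and 89%. Identical behaviour can thus put hDPP ahead on the score and dDPP ahead on completion.

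**The case against.** The strongest defence is that the settings limb has a design rationale. Sweetch is a push-delivered, sensor-driven programme, so coaching can arrive without the app being opened, and enabled permissions are a precondition for it. Counting app opens alone would class as disengaged someone who acts on notifications. This stands in part and is why the settings limb should be kept as an exposure measure. It does not make that limb equivalent to attendance. Section 6.1 says that participants who are meeting their goals may get no notification on a given day, so enabled settings show neither delivery nor response.

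A second defence is that the hDPP rules are the CDC's own and the per-protocol set is for benchmarking. That is correct for hDPP. The dDPP rule is the trial's own analogue, and the plan does compare the arms.

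Four stronger readings are tempting, and the documents do not support them:
- *That the plan enters both scores as one pooled mediator.* Section 3.1.2 states an aim, and a hypothesis that applies irrespective of arm. Section 9.4 contains no mediation model, so pooling is an inference.
- *That the definitions favour the tested product.* The settings limb raises dDPP scores, but the reduced, capped denominator raises hDPP scores.
- *That someone who never opens the app scores exactly 100%.* Download and registration need initial use, and the kit delay probably costs a week or two. An emailed download link (Section 6.1) could allow earlier installation, so 100% is possible but not shown.
- *That the engagement results are uninterpretable as a whole.* The problem is confined to cross-arm use and the dDPP completer set.

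**Conclusion.** The point holds for secondary endpoints. The dDPP score and completer status can be met without app use after set-up, whereas hDPP requires attendance. Differences in engagement and completion between arms, the mediation result and the dDPP benchmark set therefore depend partly on the metric.

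The size cannot be fixed from the documents, because they do not say how often participants will leave settings on without using the app. The 32% and 22% figures are lower ends, and the near-100% figure is an upper end. The net direction is not determined.

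The primary ITT comparison, engagement-outcome associations within an arm, and the hDPP benchmark against the CDC rule are not affected. A clarification in the analysis plan is enough; the design need not change.

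**What to change.** 1. Keep the planned scores as descriptive outputs.
2. Pre-specify an active-use dDPP score and completer definition based only on in-app access, and report the settings limb separately as exposure.
3. Present between-arm engagement, completion, the 60% benchmark and mediation under both definitions, and state in Section 9.4 the mediation model and how each score enters it.
4. State that the raw percentage difference between arms will not be read as a difference in behaviour.
5. If a common metric is wanted, such as months with at least one active contact, label it supportive. Count it from the first available session or from app installation. Section 6.4 allows a lag of up to 4 weeks to an available session and encourages a start within 8. On a clock starting at randomisation, a late hDPP starter could lose month 1 and reach at most 5/6 = 83%.

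**Cost.** Analysis-plan wording and one extra set of results. App logs (Sections 3.1.3 and 6.4) and dated session records (Section 11.13) are already collected. Two downsides should be stated. The active-use score undercounts people who respond to notifications without opening the app. Any common metric also departs from the CDC definition and equates unlike contacts: one app opening a month for six months would score the same as attending all 16 core sessions.

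### As literally written, the hDPP months 1-12 engagement score lets surplus sessions in one phase offset missed sessions in the other, so a participant with no maintenance sessions can score 100% for the year

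*Combined protocol and SAP*

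**What the plan says.** Section 3.3 (Secondary Endpoints) defines the hDPP engagement score as a percentage of sessions attended and fixes the denominators: "the number of required hDPP sessions for months 1-6, 7-12, and 1-12 will be 8, 3, and 11, respectively". Section 3.1.2 gives the same denominators ("Percentage engagement will be defined out of a total of 8 sessions in month 1-6 and 3 sessions in month 7-12") without mentioning a cap, and ties the definition to the CDC engagement definitions current when the study is completed.

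The cap appears only in Section 3.3: "For participants who attend more than the required number of sessions across each of these intervals, the engagement score will be capped at 100" per cent. The example that follows it, with 4 sessions in months 1-6 and 1 in months 7-12, ends with a year score of "45% (5 out of 11 sessions in months 1-12").

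The year score is one of three analysed: "Engagement will be analyzed across months 1-6, 7-12, and 1-12 months".

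On supply, Section 6.2 states that "each site offers at least 16 sessions during the first 6 months (core phase) and 6 sessions during the last 6 months".

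The dDPP score in Section 3.3 is the percentage of full weeks on study in which an app-use criterion is met. The section's example has 25 full weeks in months 1-6 and 26 in months 7-12.

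**The concern.** The plan sets a separate requirement for each half-year, and each half-year score gives no credit beyond its own requirement. The year score, on its literal wording, does not carry that principle over. It adds all sessions, divides by 11 and cuts the result off at 100%. Because programmes offer twice the required number of core sessions, the full 11 can be reached before month 7.

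Two things are at stake. First, a year score of 100% need not mean that both half-year requirements were met, so the three scores reported for one participant can read 100%, 0% and 100%. Second, engagement is to be compared between arms, and the offsetting is possible in only one of them. A week of app use in months 1-6 cannot stand in for a week missed in months 7-12, because engaged weeks cannot exceed the weeks available in each half.

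**Working it through.** **Inputs.** Required sessions 8, 3 and 11 (Sections 3.3 and 3.1.2); at least 16 core and 6 maintenance sessions offered (Section 6.2); 25 + 26 = 51 full weeks in the dDPP example (Section 3.3). Write c for sessions attended in months 1-6 and m for sessions attended in months 7-12.

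**Formulas.**
- Half-year scores: min(100%, c/8) and min(100%, m/3).
- Year score, literal reading: min(100%, (c + m)/11).
- Year score, counts capped by phase: [min(c, 8) + min(m, 3)]/11.

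**Reproducing the plan's example** (c = 4, m = 1). 4/8 = 50.0%, 1/3 = 33.3%, 5/11 = 45.5%, matching the printed 50%, 33% and 45%. The simple mean of the half-year scores would be (50.0 + 33.3)/2 = 41.7%, so the year score is not that mean. Capping by phase also gives (4 + 1)/11 = 45.5%, because the example has no surplus sessions. It therefore cannot show which year formula is meant.

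**Cases where the two formulas can differ** (scores in %, differences in points):

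| c | m | Months 1-6 | Months 7-12 | Year, literal | Year, capped by phase | Difference |
|---|---|---|---|---|---|---|
| 8 | 0 | 100 | 0 | 72.7 | 72.7 | 0 |
| 9 | 0 | 100 | 0 | 81.8 | 72.7 | 9.1 |
| 10 | 0 | 100 | 0 | 90.9 | 72.7 | 18.2 |
| 11 to 16 | 0 | 100 | 0 | 100 | 72.7 | 27.3 |
| 10 | 1 | 100 | 33.3 | 100 | 81.8 | 18.2 |
| 5 | 6 | 62.5 | 100 | 100 | 72.7 | 27.3 |
| 8 | 3 | 100 | 100 | 100 | 100 | 0 |

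Eleven of 16 core sessions is 11/16 = 69% core attendance. The c = 5, m = 6 row shows that the offset also runs the other way.

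**Largest difference with 16 and 6 sessions offered.** If c is at least 8, the capped score is at least 8/11, so the difference is at most 3/11. If c is below 8, only surplus maintenance sessions count, and there are at most 6 - 3 = 3, so the limit is again 3/11 = 27.3 points. The literal score is never below the capped one.

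**Consistency with the half-year scores.** In the plan's example the year score equals the half-year scores weighted 8:3, since 8/11 x 50% + 3/11 x 33.3% = 45.5%. For c = 11, m = 0 the same weighting gives 8/11 x 100% + 3/11 x 0% = 72.7%, while the literal rule gives 100%. Capping by phase keeps the weighting true for every participant.

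**The other arm.** A dDPP participant engaged in all 25 full weeks of months 1-6 and in none afterwards scores 25/51 = 49% for the year.

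**The case against.** The strongest reply is that the cap sentence refers to each of the intervals, and so could be read as crediting at most 8 and 3 sessions before pooling. That reading is possible, and the example does not exclude it. But the sentence caps a score, not a count, and no other section limits the counts. Two analysts could code different year scores from this text, which is itself a reason to settle it.

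A second reply is that a pooled count is a legitimate dose measure. Section 2.2 links outcomes to the number and frequency of sessions attended as well as to duration in the programme. Capping by phase also loses information: 8, 9, 10 and 11 or more core sessions without maintenance all become 72.7%. This stands as a real but small cost. The months 1-6 score already discards the same gradation, and the literal year score discards it above 11.

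Third, the drop-off is not hidden. The separate months 7-12 score is 0% for the participant with no maintenance sessions. That limits the damage but does not correct the year score.

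Two stronger readings are tempting, and the documents do not support either.
- A reader might infer that the score contradicts completer status, since completers are those "whose time from first session held by the cohort to the last session attended by the participant is at least 9 months" as well as attending at least 8 sessions in months 1-6. But the two measures ask different things and can diverge under either formula. Eight core sessions plus three maintenance sessions by month 8 score 100% even when capped by phase, yet fall short of 9 months. Eight core sessions plus one at month 10 meet the completer definition at 9/11 = 81.8%.
- A reader might infer that the engagement-outcome association within hDPP is attenuated. Section 3.1.2 does not say which interval's score enters the association or mediation analysis, and Section 9 specifies no mediation model. Which formula tracks outcome better is an empirical question.

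**Conclusion.** The point holds as a minor defect in one derived score. On the literal wording of Section 3.3, surplus sessions in one phase can offset missed sessions in the other, so the hDPP year score can reach 100% with 0% for months 7-12, or with 62.5% for months 1-6. With 16 core and 6 maintenance sessions offered, the gap from a phase-capped score is at most 27.3 points. That figure is the distance between two scoring rules, not an error measured against a known truth.

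Because the literal score is never lower than the phase-capped one and the dDPP score has no equivalent carry-over, the rule can only raise the hDPP year score relative to dDPP or leave it unchanged.

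The conclusion rests on taking the cap as applying to each interval's final score, and on the session numbers in Section 6.2, which are minima. The documents give no attendance distribution, so neither the number affected nor the effect on the between-arm comparison or the engagement-outcome association can be calculated. The primary endpoint and the sample size are unaffected.

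**What to change.** In Section 3.3, define the months 1-12 hDPP score as [min(sessions in months 1-6, 8) + min(sessions in months 7-12, 3)] / 11, and refer to that definition from Section 3.1.2. If updated CDC session requirements are adopted at study completion, put the new numbers in place of 8, 3 and 11 and keep the cap by phase. The worked example stays at 45%, and 100% then requires both half-year requirements to be met.

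The cost is one line of text, preferably settled before engagement data are analysed. No new data are needed, because the local DPP form in Section 11.13 already records session type and date. Gradation above 8 core sessions is lost; to retain it, use the uncapped total number of sessions as a sensitivity dose measure.

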## 6 STUDY INTERVENTION

### 6.1 STUDY INTERVENTION DESCRIPTION

Participants randomized to the dDPP will receive the Sweetch digital health kit (app log in instructions and Bluetooth-enabled digital scale) within 8-12 days via mail. The rationale for mailing the digital health kit is to allow participants to obtain baseline PA measurements prior to starting the intervention, and also to replicate the real-world experience in which there would likely be some delay between prescriber ordering of the dDPP and patient receipt of the product.

The referral process to the Sweetch dDPP will be generated in a RedCap database, with an automated email sent to Sweetch Health, Ltd. The RedCap referral will include the following participant identifiers at the time of the referral:

[figure not shown]
- First Name
- Last Name
- Email Address
- Phone Number
- Baseline Weight
- Baseline BMI
- Laboratory measure(s) that rendered the participant eligible for the DPP (A1C, fasting glucose, plasma glucose after 75 gram OGTT) and date of the relevant lab result(s)

This will allow the Sweetch support team to contact the participant directly in the event that the user has any technical difficulties installing the app and/or syncing the Bluetooth enable digital body weight scale. A maximum of 5 communication attempts will be made directly by Sweetch to register the participant in the app. Baseline weight, BMI, and A1C data are provided to the dDPP arm as this information is also required for referral to the hDPP arm.

[figure not shown]
The Sweetch app uses self-tracking and multiple evidence-based persuasive eCoaching strategies, which have been described in detail in a recent review of automated technologies seeking to promote behavioral change. Notably, not only does the app itself employ multiple persuasive systems design elements, but the adaptive push notifications do as well: reduction (breaking down goals into smaller goals), tunneling (guiding user step by step), tailoring, personalization (continuously tuning goals and messages based on past real-world compliance and capabilities), simulation, praise, reminders, suggestion, competition, recognition, education and goal-setting.

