The Sweetch AI algorithm is used in several app components to deliver just-in-time support and/or adapt recommendations or goals in real-time based on the user's response. For example, push notifications will be sent when the algorithm detects that the user is potentially available and able to act upon the recommendation, based on various parameters including location, previous response, calendar availability, and weather, etc. These tailored pushed notifications motivate participants to meet the PA goal of 150 minutes per week, lose 5% of body weight, monitor meals and drinks, and complete the 19 CDC in-app diabetes prevention lessons for the core phase (months 1-6) and 6 in-app lessons for the core maintenance phase (months 7-12). A maximum of 10 push notifications will be sent per day; however, participants who are meeting their goals may not receive any notifications on a given day. In some instances, notifications/reminders will be sent via email mainly for educational content and technical support. For example, an email will be sent to participants upon referral to the dDPP providing the user a link to download the Sweetch app and instructions on how to complete the registration process. Also, for some participants, emails may be sent to supplement the education provided via the in-app lessons. Participants will be able to turn off/on push notifications at any time within the Sweetch app, but will not be able to make modifications to the frequency or timing of the notifications as these are generated using AI technology and are continuously adapted based on the participant's behavioral patterns and progress in the program.

[figure not shown]
This screenshot shows an example of the Sweetch personalized push notification, and home screen with goal tracking (PA, weight, in-app lessons, and habits):

This screenshot shows the main page of the app and the T2D Prevention Lessons based on the CDC curriculum. Participants are reminded to take the in-app lessons:

This screenshot shows the participant achievements, a form of social support:

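### The dDPP engagement score counts weeks from the baseline visit, before the kit is due; unless the app is installed earlier, perfect use scores at most 92–96% in months 1–6

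*Combined protocol and SAP*

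**What the plan says.** Section 3.3 (Secondary Endpoints) defines the dDPP score as "calculated as the percentage of full weeks during which the app was installed and a) both push notifications and motion sensors were enabled", or any app content was accessed. For the denominator, "full weeks will be defined as the number of complete weeks between baseline visit and the 6 month or 12 month visit, respectively". The worked example there takes 25.4 and 26.2 weeks of follow-up and says the participant "would be considered to have 25 and 26 full weeks on study, respectively". Section 3.1.2 gives the same score without saying when the count of weeks begins.

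Section 6.1 says dDPP participants "will receive the Sweetch digital health kit (app log in instructions and Bluetooth-enabled digital scale) within 8-12 days via mail". One stated reason for mailing is "to allow participants to obtain baseline PA measurements prior to starting the intervention"; the other is to mimic the delay a patient would meet in practice. The Schedule of Activities also lists kit mailing and app download after the baseline visit. Section 6.1 adds, however, that "an email will be sent to participants upon referral to the dDPP providing the user a link to download the Sweetch app", and does not say whether installation should wait for the kit.

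For hDPP, Section 3.3 divides sessions attended by a fixed 8 (months 1–6), 3 (months 7–12) or 11 (months 1–12), capped at 100%. Section 6.2 says programs offer at least 16 core sessions in the first six months.

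**The concern.** The design schedules one to two weeks in which a dDPP participant is not meant to have the program, and the score then treats those weeks as weeks without engagement. Nothing in the documents removes them from the denominator or says how a week counts when the app is available for only part of it. A late start in the hDPP arm does not lower that arm's maximum.

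Comparing engagement between arms, and testing whether engagement mediates clinical differences, are secondary objectives (Sections 1.1 and 3.1.2). Section 2.2 expects greater engagement with dDPP. An offset that comes from delivery timing works against that hypothesis and puts a non-behavioural difference between arms into the mediator.

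**Working it through.** **Inputs.** Full weeks: 25 or 26 (example in Section 3.3). Kit lag: 8–12 days (Section 6.1), taken from the baseline visit as day 0 because the documents do not state the starting point. Sample size: 184 randomised per arm, 138 after the planned 25% attrition (Section 9.2). Assumptions that are not in the documents: mean engagement of 50–60% once the app is available, and an SD of the score of 30–40 points.

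**1. The plan's own figures.** Rounding down, 25.4 gives 25 and 26.2 gives 26. The hDPP example gives 4/8 = 50%, 1/3 = 33% and 5/11 = 45%. All reproduce.

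**2. Weeks lost before the kit.** A lag of 8–12 days leaves week 1 wholly uncovered and week 2 partly covered. So k = 1 week is lost if a partly covered week counts, and k = 2 if it does not.

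**3. Maximum dDPP score, (W − k)/W, where W is the number of full weeks.**
- Months 1–6, W = 25: 24/25 = 96.0% or 23/25 = 92.0%.
- Months 1–6, W = 26: 25/26 = 96.2% or 24/26 = 92.3%.
- Months 1–6 with the ±14-day window around day 180 (W = 23 to 27): from 21/23 = 91.3% to 26/27 = 96.3%.
- Months 1–12, W = 51: 50/51 = 98.0% or 49/51 = 96.1%.
- Months 7–12: no loss, if that window starts at the 6-month visit.

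**4. Sensitivity to timing.** If the app were installed on day 0 through the referral email, k = 0 and the maximum is 100%. If instead the baseline visit fell up to 14 days before day 0 and the 8–12 days ran from day 0, the lag would reach 22–26 days. Then k = 3 or 4, and the maximum is 22/25 = 88% or 21/25 = 84%.

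**5. The same check for hDPP.** With weekly core sessions and a start 4 weeks late, 25 − 4 = 21 weeks remain, more than enough for 8 sessions. At 8 weeks late, 17 remain. The maximum stays at 100%.

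**6. Average offset between arms.** A participant engaged in a proportion p of the available weeks scores p(W − k)/W, so the loss is p × k/W. With W = 25 that is p × 4 or p × 8 points. At p = 0.5 the loss is 2–4 points; at p = 0.6 it is 2.4–4.8 points. Someone who never installs loses nothing.

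**7. In standard errors.** SE = SD × √(2/n).
- n = 184: 30 × 0.104 = 3.1; 40 × 0.104 = 4.2.
- n = 138: 30 × 0.120 = 3.6; 40 × 0.120 = 4.8.

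The ratio runs from 2/4.8 = 0.4 to 4.8/3.1 = 1.5.

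**The case against.** The strongest reply is that counting the delay is deliberate. Section 6.1 gives real-world delay as a second reason for mailing the kit, Section 4.1 frames the trial as real-world effectiveness, Section 6.4 times outcomes from randomisation, and Section 3.3 applies the baseline-visit clock to both arms. A score that includes start-up delay is a defensible quantity. But this justifies delaying delivery. It does not justify reading the delay as participants not engaging, and the hDPP score does not charge its own start-up lag in the same way.

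Two further objections stand and limit the point. The ceiling is conditional: the referral email may allow installation before the kit arrives. And the 92% end depends on how a partly covered week is treated. Since opening any content earns the week, a single access late in week 2 might count, which would leave 96%.

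It is also fair that the remedy gives up the common starting point and adjusts for delay in one arm only. The hDPP lag needs no matching correction for the ceiling, as step 5 shows.

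**Conclusion.** The point holds, conditionally and at modest size. If the app is not installed before the kit arrives, the dDPP score cannot exceed 92–96% in months 1–6 (25 full weeks, kit lag counted from the baseline visit) or about 96–98% over months 1–12, while hDPP can reach 100%. The average offset is about 2–5 points in months 1–6, or roughly 0.4–1.5 standard errors, under the assumed use and SD. The primary endpoint, the sample size and the completer rule are unaffected.

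Three stronger readings are tempting, and the documents do not support them:
- *The arms differ by a built-in 4–8 points.* That is the loss for a perfect user only. Nor can it be set against an SD of 30–40: on a 0–100 scale with mean m the SD cannot exceed √(m(100 − m)), which is 19.6 at m = 96 and 27.1 at m = 92.
- *The ceiling is certain.* The referral email leaves earlier installation open.
- *The dDPP completer rule contradicts the engagement score.* That rule requires participants "whose time between app installation and last week of engagement is at least 9 months", so its clock starts at installation. It is a separate endpoint modelled on the hDPP completer rule, which runs from the cohort's first session. Different clocks for different endpoints are not a contradiction.

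**What to change.** In Sections 3.3 and 3.1.2:
- Start the dDPP denominator for months 1–6 and 1–12 at one fixed, schedule-based study day after planned kit delivery, the same for everyone randomised to dDPP. If the 8–12 days run from the baseline visit, day 14 is the first week boundary after day 12. Perfect use then scores 23/23 = 100%. Because the start does not depend on actual installation, participants who never install still score 0.
- Count numerator weeks in the same window, and state how a partly covered week counts.
- Keep the score counted from the baseline visit as a sensitivity analysis.
- Reconcile the kit timing, the referral email and the Schedule of Activities on when installation can occur, and state the day from which the 8–12 days are counted.

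The cost is a few sentences and a changed start date in the app-log programming. The dDPP window becomes one to two weeks shorter and no longer shares its start with the baseline visit. Because the study team sees the app logs in real time (Section 6.4), the change should be dated and made before engagement is compared by arm.
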